Unique Protocol ID: DCM-AHEAD

**Brief Title: Diabetes and Lipid Accumulationand Heart Transplant
(DCM-AHEAD)**

Official Title: Lipid Accumulation in Heart Transplant From Non-diabetic Donors to Diabetic Recipients

Project manager: [name]

Department of Advanced Medical and Surgical Sciences

[contact]

e-mail: [contact]

clinical trial number: NCT03546062

clinical trial registry: clinicaltrialgov.com

Naples November 19, 2019

BACKGROUND

[figure not shown]
Idiopathic dilated cardiomyopathy (IDC) is defined by the presence of left ventricular systolic dysfunction in the absence of an abnormal loading condition or significant coronary heart disease (1). IDC is the leading cause of end-stage heart failure (HF) and is responsible for half of all heart transplants (HTx) (1). Endocrine disorders, including diabetes, are known to be associated with IDCs. Diabetes mellitus (DM), which is present in 75% of patients with idiopathic IDC, is an independent risk factor for the development of heart failure and death in IDC (2-4). Therefore, DM may exacerbate the need for HTx; moreover, diabetic patients are less suitable for HTx and DM remains an independent risk factor for death even after HTx (5). Recent studies have revealed the presence of diabetic cardiomyopathy, a condition of myocardial dysfunction without coronary heart disease (6, 7). This term was first introduced by Rubler et al. (8) in 1972, which highlighted patients with diabetes and congestive heart failure with normal coronary arteries. The pathophysiological mechanisms by which diabetes affects the development and progression of diabetic heart disease are not known. Therefore, the aim of our study will be to evaluate, in the diabetic heart removed, the presence of any cellular alterations related to diabetic disease. In addition, the progression of such lesions in the transplanted heart in diabetic patients will be evaluated.

MATERIALS AND METHODS

Study protocol

A prospective observational study will be conducted with a follow-up duration ranging from a minimum of 12 months to a maximum of 36 months (Figure).

STUDY PROTOCOL

Patients

A cohort of consecutive patients (diabetics vs. non-diabetics) with IDCM and NYHA class III/IV heart failure refractory to maximum medical therapy and treated with cardiac transplantation at the Division of Cardiac Surgery of the University of Campania "Luigi Vanvitelli" will be evaluated prospectively. At the Department of Medical Sciences will be conducted the clinical follow-up for cardiometabolic evaluation (eg routine, glycemic compensation). The molecular and cellular study will be conducted at the department of biochemistry. The follow-up will be 12 months. Patients will be recruited aged > 18, <75 years, with indication to receive a heart transplant (survival score for accepted heart failure (HFSS) at high risk, peak VO₂ <10 ml / kg / min after reaching the anaerobic threshold; recurrent symptomatic ventricular arrhythmias refractory to medical treatment, ICD and surgical), affected by IDCM with heart failure in class III / IV NYHA refractory to maximal medical therapy; diabetic and non-diabetic patients. Patients with non idiopathic dilated heart disease (valvular disease, ischemic-infarct heart disease, etc.) will be excluded. All patients will be included in the study after signing the informed consent to participate in the study. The study will be performed according to the Helsinki Declaration.

Explanted heart analysis

Myocardial tissues from hearts removed from diabetics vs. non-diabetics will be analyzed from a histological, microscopic and metabolic functional point of view. From the residual portion of the heart removed, after routine histological analyses conducted according to the "Heart Transplant Clinical Guidelines 2017". (9), a portion of muscle tissue (quantity 5-10 mm³) will be removed, from which 3 portions will be obtained: one portion will be incorporated into the OCT compound for immunohistochemical analysis, a second portion will be immediately frozen in liquid nitrogen and stored at -70°C for WB evaluation, and a third portion will be used for quantitative evaluations performed by ELISA.

Endo-myocardial biopsies and Follow up

Transplanted patients will be followed through an echocardiographic evaluation (enrolment and 3-6-12 months follow-up), to evaluate cardiac functional parameters, metabolic parameters and survival outcomes (death for all causes, cardiac death, re-hospitalisation for heart failure). In all transplanted patients endo-myocardial biopsies (EMB) are collected according to normal clinical practice by the "ASHI" guideline (9): weekly for the first month; every 2 weeks for the following month; 1 for the following 4 weeks; 1 for the following 6 weeks; every 3 months for the following 2 years; and finally every 6 months for the following 3 years. 2-6 (usually 4, 1 to 3 mm³) fragments of myocardial tissue will be collected from the apical segment of the right side of the interventricular septum (IVS). The collected myocardial tissue will be immediately analyzed for histopathological evaluation of rejection. From the remaining portion of tissue 3 portions will be obtained: one portion will be incorporated into the OCT compound for immunohistochemical analysis, a second portion will be frozen immediately in liquid nitrogen and stored at -70°C for PCR evaluation, and a third portion will be used for quantitative evaluations performed by ELISA. The conservation and morpho-functional evaluation of biopsy samples will be carried out at the Bio-Bank of the University of Campania "Luigi Vanvitelli".

Biopsies analysis

PCR.

Total RNA will be isolated from human heart sample homogenates using the RNeasy Mini kit (74106, Qiagen), according to the manufacturer's protocols "Stabilization of RNA in collected animal tissues" and "Purification of total RNA from animal tissues". RNA concentration and purity will be determined using the NanoDrop 2000c (Thermo Fisher Scientific) spectrophotometer. Genomic DNA (gDNA) contamination will be removed from RNA samples prior to the Reverse Transcription (RT) phase, performed on the Gene AMP PCR System 9700 (Applied Biosystems)

using the QuantiTect Reverse Transcription Kit (205311, Qiagen), according to the "Reverse Transcription with Elimination of Genomic DNA for Quantitative, Real-Time PCR" protocol. The final step for real-time PCR analysis (qPCR) will be performed on the CFX96 Real-time System C1000 Touch Thermal Cycler (BIORAD). The analysis will be performed according to the "Two-Step RT-PCR (Standard Protocol)" protocol, using the QuantiTect SYBR Green PCR Kit (204143, Qiagen) and specific QuantiTect Primer Assays (249900, Qiagen) for each gene tested. Relative quantization of gene expression will be performed using the $2^{-\Delta\Delta Ct}$ method, using GAPDH as the cleaning control gene. P values will be calculated on the basis of a student t-test or one-way variance analysis (ANOVA), followed by Dunnett's post hoc test; $P < 0.05$ will be considered significant.

Immunofluorescence. Confocal laser scanning microscopy.

The analysis of immunofluorescence in sections of the myocardium will be performed according to the manufacturing protocol using the laser scanning confocal microscope (LSM 700; Zeiss). In particular, the complete removal of the paraffin will be carried out before proceeding to the staining of the section. For this purpose, the slides will be deparaffinized by passing them through xylenes, alcohols and water. An antigen recovery buffer (10 mM sodium citrate, 0.05% Tween 20, pH 6.0) will be added to the dewaxed and rehydrated sections and boiled in the microwave for 20 minutes. After 20 minutes, immunofluorescence staining will be performed using specific antibodies against PPAR-alpha (1 μ g/ml) (polyclonal rabbit, NB600-636, Novusbio, Abingdon, UK), PPAR-gamma (1 μ g/ml) (mouse monoclonal, orb69095, Biorbyt, Cambridge, UK) or against SREBP1 (1 μ g/ml) (polyclonal rabbit, ab28481, Abcam, Cambridge, UK). Secondary antibodies will be conjugated with Alexa Fluor 633 or Alexa Fluor 488 (Life Technologies Italia, Monza, Italy). Nuclear contrast staining will be performed using the VECTASHIELD® mounting medium with DAPI (H-1200, Vector Laboratories, Burlingame, USA).

Immunohistochemistry.

Oil Red O (Solvent Red 27, Sudan Red 5B, C.I. 26125, C26H24N4O) will be used for the assessment of the accumulation of intramyocytic lipids.

Statistical analysis

Study population groups (diabetics vs. non-diabetics) will be compared using the Pearson test for categorical variables and the Kruskal-Wallis test for continuous variables. Candidates for admission to the multivariate model will be identified by focusing on factors that will differ significantly (P value < 0.05) in the univariate analysis among diabetic vs non-diabetic patients. Cox regression will be used to construct the predictive model of mortality. The risk ratio for mortality will be adjusted by age, BMI, cholesterol, LDL, triglycerides and aspirin, ticlopidine, anti-aggregants, beta-blockers, ACE inhibitors or tailors, antidiabetic drugs, statins, etc. present at the time of admission to hospital for cardiac transplantation. The analysis of survival after cardiac transplantation will be performed using the Kaplan-Meier curve and the Cox regression method. Mortality curves will be obtained separately for diabetic and non-diabetic patients, and then compared using the log-rank test. All tests will be considered significant if they have a value of $p < 0.05$. All tests will be conducted in 2 populations: diabetic vs non-diabetic patients after cardiac transplantation. The SPSS program (version 21, IBM SPSS) will be used for all analyses.

References

2. L López-Sainz Á, Barge-Caballero E, Barge-Caballero G, Couto-Mallón D, Paniagua-Martin MJ, Seoane-Quiroga L, Iglesias-Gil C, Herrera-Noreña JM, Cuenca-Castillo JJ, Vázquez-Rodríguez JM, Crespo-Leiro MG. Late graft failure in heart transplant recipients: incidence, risk factors and clinical outcomes. *Eur J Heart Fail.* 2018;20:385-394.

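### PCR results on the post-transplant biopsies are normalised to GAPDH alone, so any GAPDH difference between diabetic and non-diabetic recipients would shift every gene's fold change, and nothing planned would reveal it

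*Combined protocol and SAP*

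**What the plan says.** The PCR part of the Biopsies analysis section sets one rule for relative expression: "Relative quantization of gene expression will be performed using the $2^{-\Delta\Delta Ct}$ method, using GAPDH as the cleaning control gene". The word cleaning is evidently a translation of housekeeping. The rule covers all targets, since the section foresees "specific QuantiTect Primer Assays (249900, Qiagen) for each gene tested" without listing the genes. Testing follows in the same section: "P values will be calculated on the basis of a student t-test or one-way variance analysis (ANOVA), followed by Dunnett's post hoc test", at the 0.05 level.

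The contrast is given under Statistical analysis: "All tests will be conducted in 2 populations: diabetic vs non-diabetic patients after cardiac transplantation".

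The tissue for PCR is set under Endo-myocardial biopsies and Follow up, where the frozen portion of each graft biopsy goes to PCR. Under Explanted heart analysis the frozen portion goes to WB instead.

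The checks described before quantification are RNA concentration and purity by spectrophotometer and removal of genomic DNA. No section names a second reference gene, a comparison of GAPDH Ct between groups, or an analysis with another normaliser.

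**The concern.** The 2^-ddCt measure reads each target against the reference gene. It estimates a group difference in the target only if the reference is equally expressed in the two groups. That GAPDH is an enzyme of glucose breakdown is textbook biochemistry. The exposure here is recipient diabetes, so the assumption is least secure in the comparison the study wants to make.

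If it fails, the error is systematic. It enters every gene by the same amount on the log scale. It can make unchanged genes look altered, or mask or reverse a true change. Several genes moving together would look like mutual support when they only share a denominator. A larger sample or a different test does not remove it.

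**Working it through.** The documents give no sample size, effect size or Ct standard deviation (SD), so there is no planned figure to reproduce. The values of d, n and SD below are assumptions, shown as ranges.

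**Step 1: the identity.** Let d be the mean GAPDH Ct in diabetic recipients minus that in non-diabetic recipients.

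ddCt = (Ct target - Ct GAPDH) in diabetics - (Ct target - Ct GAPDH) in non-diabetics.

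For a target with no true difference, ddCt = -d, and the apparent fold change is 2^-(-d) = 2^d.

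- d = 0: 1.00
- d = 0.3: 2^0.3 = 1.23
- d = 0.5: 2^0.5 = 1.41
- d = 1.0: 2^1 = 2.00

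Negative d gives the reciprocals (0.71 for -0.5, 0.50 for -1.0). Masking works the same way: a true halving with d = +1.0 is reported as 0.5 x 2 = 1.0. A GAPDH shift common to both groups cancels.

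**Step 2: false positives for an unchanged gene.** Assume one value per patient, a two-sided 5% test (the plan does not state sidedness), a normal approximation and SE = SD x sqrt(2/n). The rejection rate is 1 - Phi(1.96 - d/SE) + Phi(-1.96 - d/SE).

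Example with n = 20 per group, SD of dCt 1.0 and d = 0.5: SE = sqrt(2/20) = 0.316 and d/SE = 1.58. The rate is 1 - Phi(0.38) + Phi(-3.54) = 0.353.

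With SD 1.0:

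| n per group | d = 0 | d = 0.25 | d = 0.5 | d = 1.0 |
|---|---|---|---|---|
| 10 | 5.0% | 8.6% | 20.1% | 60.9% |
| 20 | 5.0% | 12.4% | 35.3% | 88.5% |
| 50 | 5.0% | 24.0% | 70.5% | 99.9% |

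At n = 20 and d = 0.5 the rate is 88.5% with SD 0.5 and 18.4% with SD 1.5. For any non-zero d the rate rises with n.

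**Step 3: shared error.** A simulation of 20,000 runs took three unchanged genes normalised to one GAPDH value, with n = 20, SD 1.0 and d = 0.5. It gave about 34% false positives per gene, 59% for at least one and 12% for all three. Independent errors at 34% would give 0.34 x 0.34 x 0.34 = 3.9% for all three. With d = 0 the simulated figures are 5%, 13% and 0.3%.

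**Step 4: would averaging GAPDH with other genes be enough?** With k reference genes averaged on the Ct scale and only GAPDH shifting, the bias is d/k. For d = 0.5, n = 20 and SD held at 1.0:

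- k = 1: fold change 1.41, false positives 35.3%
- k = 2: 2^0.25 = 1.19, 12.4%
- k = 3: 2^0.167 = 1.12, 8.2%

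Averaging dilutes the bias but does not remove it. Leaving GAPDH out of the primary normaliser removes this source.

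**The case against.** The strongest objection is that the premise is empirical and the documents do not supply it. They do not say that GAPDH expression differs between the groups, in which direction, or by how much. Disturbed glucose metabolism does not by itself show that it does. This stands: a reader might infer that the PCR results will be wrong, and the documents do not support that. They support only the conditional statement and the absence of any safeguard.

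A reader might also infer that PCR compares natively diabetic with non-diabetic hearts, because the protocol says "Myocardial tissues from hearts removed from diabetics vs. non-diabetics will be analyzed from a histological, microscopic and metabolic functional point of view". That sentence concerns the explanted hearts, whose frozen portion is assigned to WB. The PCR text refers generally to heart samples, but the only tissue assigned to PCR is the graft biopsy, and the official title describes non-diabetic donors for the diabetic recipients. The relevant shift is therefore one that arises in the graft under a diabetic recipient, which is a less direct route.

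The ddCt calibrator is not specified. If it were each graft's own early biopsy, a constant group difference in GAPDH would cancel. A difference that developed over follow-up would not, and progression in the transplanted heart is among the study's stated aims.

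The reach is also limited. Lipid accumulation is read by Oil Red O, and the PPAR and SREBP1 proteins by immunofluorescence. Neither these nor ELISA, echocardiography or survival use GAPDH normalisation under this plan. An inference that the main lipid result is compromised would be wrong.

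Finally, GAPDH Ct will exist for every PCR sample, so a later comparison at known RNA input is possible. That lowers the urgency, but the plan does not call for it, and without a second gene there would be no alternative normaliser to fall back on.

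**Conclusion.** The point holds in conditional form and for the PCR results only. A single glycolytic reference gene is used to compare groups defined by diabetes, with no planned means of seeing whether it differs between them. A Ct difference of d multiplies every fold change by 2^d or 2^-d: 1.23, 1.41 and 2.00 (or their reciprocals) for d of 0.3, 0.5 and 1.0, and nothing at d = 0.

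The multiplier follows exactly from the plan's own formula once d is given. The false-positive rates rest further on the assumed n and SD and illustrate scale; they do not predict this study's error. Not every gene need cross the 0.05 line, because the shift adds to whatever true effect and noise each gene has.

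**What to change.** Before any target gene is analysed, amend the PCR section as follows.

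1. Name the primary normaliser: the mean Ct (geometric mean expression) of one or, preferably, two reference genes outside glucose and lipid metabolism, for example a ribosomal gene, run on the same cDNA as the targets.
2. Report GAPDH-normalised results as a sensitivity analysis.
3. Report each reference gene's Ct by group at equal RNA input, with a confidence interval for the difference. RNA concentration is already to be measured, so this is feasible.
4. Do not use a significance test to decide whether GAPDH is kept. Such a rule depends on the data, and in a small sample a non-significant difference does not show equality.

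The new genes' stability is also an assumption. That is why two are better than one and why item 3 covers all of them.

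The cost is one or two extra primer assays, a few lines of text and slightly more cDNA. The biopsy fragments are 1 to 3 mm³, go first to rejection histology, and the remainder is split three ways. The reference panel should therefore be fixed before the cDNA is used up. No extra biopsy is needed.

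### The PCR p-values use the equal-variance Student t-test although nothing secures equal group sizes; if size and spread both differ, the error rate leaves 5% in an unknown direction

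*Combined protocol and SAP*

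**What the plan says.** The PCR paragraph under Biopsies analysis reads: "P values will be calculated on the basis of a student t-test or one-way variance analysis (ANOVA), followed by Dunnett's post hoc test". The threshold is P < 0.05; sidedness is not stated. The paragraph names no unequal-variance version of any of these tests. It quantifies expression by the 2^-ddCt method but does not say whether the test is run on the Ct scale or on fold changes.

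The Patients section describes "A cohort of consecutive patients (diabetics vs. non-diabetics) with IDCM", with no ratio, quota or matching. No sample size, group size or SD appears anywhere.

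Two statements in the Background bear on the split. One is "Diabetes mellitus (DM), which is present in 75% of patients with idiopathic IDC". The other says that diabetic patients are less suitable for transplantation.

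The Statistical analysis section sets the same 0.05 level for all tests, limits them to two populations (diabetic and non-diabetic), and names Kruskal-Wallis for continuous variables. It does not say how that rule fits with the t-test named for PCR.

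**The concern.** The Student t-test, one-way ANOVA and Dunnett's test all estimate a single variance from all groups together. For two groups that does little harm if sizes are about equal or if spreads are equal. Otherwise the larger group dominates the pooled estimate:

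- If the larger group is the more variable, the standard error is too big and real expression differences are missed.
- If the smaller group is the more variable, the standard error is too small and false differences are declared.

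Consecutive enrolment leaves the sizes to chance and referral. Unequal spread is plausible but undocumented: the diabetic group mixes patients with different glycaemic control and antidiabetic drugs. At stake is whether a PCR p-value below 0.05 carries its stated meaning, and whether the study can see a real difference.

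**Working it through.** **Inputs.** From the documents: Student t-test, level 0.05, two populations, consecutive enrolment. Assumed because the documents are silent: two-sided testing, 40 patients in total, normally distributed values, one value per patient, and a diabetic SD of 1, 1.5 or 2 times the non-diabetic SD (set to 1).

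**Step 1: reproduce the stated level.** With equal SDs the simulated size of the Student test is 4.9% to 5.0% at every split tried, including 30 v 10 and 10 v 30. The plan's 5% is right under equal spread.

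**Step 2: large-sample formula for unequal spread.** Let n1 and s1 be the diabetic size and SD, and n2 and s2 the non-diabetic.

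- True variance of the mean difference: T = s1²/n1 + s2²/n2
- Variance the pooled test uses: P = [(n1·s1² + n2·s2²)/(n1 + n2)] × (1/n1 + 1/n2)
- Actual size = 2 × [1 − Φ(1.96 × √(P/T))]

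With s1 = 1.5 and s2 = 1:

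- 30 v 10: T = 2.25/30 + 1/10 = 0.175; P = (77.5/40) × 0.1333 = 0.2583; √(P/T) = 1.215; 1.96 × 1.215 = 2.381; size 1.7%.
- 10 v 30: T = 2.25/10 + 1/30 = 0.2583; P = (52.5/40) × 0.1333 = 0.175; √(P/T) = 0.823; 1.96 × 0.823 = 1.613; size 10.7%.
- 22 v 18: T = 0.1578; P = (67.5/40) × 0.1010 = 0.1705; √(P/T) = 1.039; 1.96 × 1.039 = 2.037; size 4.2%.
- 20 v 20: T = P = 0.1625; size 5.0%.

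**Step 3: simulation** (100,000 or 200,000 replicates per row).

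| Diabetic v non-diabetic | SD ratio | Student size | Welch size |
|---|---|---|---|
| 30 v 10 | 1.5 | 1.9% | 5.1% |
| 30 v 10 | 2 | 0.9% | 5.0% |
| 10 v 30 | 1.5 | 10.8% | 5.1% |
| 10 v 30 | 2 | 15.4% | 5.1% |
| 22 v 18 | 1.5 | 4.3% | 5.0% |
| 22 v 18 | 2 | 3.9% | 5.0% |
| 20 v 20 | 1.5 | 5.2% | 5.0% |
| 20 v 20 | 2 | 5.3% | 5.0% |

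A larger cohort at the same ratio does not help: at 20 v 60 the Student size is 10.6% (SD ratio 1.5) and 15.2% (ratio 2).

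**Step 4: power for a difference of one non-diabetic SD at 30 v 10.** SD ratio 1.5: Student 48%, Welch 63%. SD ratio 2: about 26% v 51%. Equal SDs: 76% v 73%, so Welch costs 76 − 73 = 3 points.

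**Step 5: would the Kruskal-Wallis rule repair it?** No. At 10 v 30 its size is 8.2% (SD ratio 1.5) and 10.3% (ratio 2); at 30 v 10 it is 2.8% and 2.1%.

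**Step 6: does Welch hold 5% on fold changes?** Not reliably. With identical distributions in both groups, skewed as fold changes are (log2 SD 0.7 to 1.5, assumed), at 30 v 10 and 10 v 30 Welch runs at about 6% to 7% and Student at about 4% to 5%. The repair therefore depends on testing dCt values.

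**The case against.** The strongest reply is that both conditions, unequal size and unequal spread, are assumed. The documents do not exclude a near-even split, and then the departure is trivial. No passage gives a variance for any gene. This stands, and it is why the point is conditional.

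A reader might infer from the 75% figure that the cohort will be about 3:1 diabetic. The documents do not support that. The figure describes patients with the disease, not those transplanted, and the same section calls diabetics less suitable for transplantation, so the ratio could be closer to even or reversed.

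A reader might also infer that the PCR results will carry too many false positives. That does not follow either. If the 75% split did hold and diabetics were the more variable group, the Student test would be conservative: power would be lost and no false positives added. Inflation needs the smaller group to be the more variable one.

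It can also be said that larger gaps sit nearby. Endo-myocardial biopsies and Follow up schedules many biopsies per patient, and no unit of analysis is stated. Treating four biopsies per patient as independent, with 20 patients per group and equal SDs, gives a type I error of about 12% at an assumed intraclass correlation of 0.2 and about 22% at 0.5. Welch does not correct that. This too stands: it limits what the change delivers but gives no reason to keep the pooled test.

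**Conclusion.** The point holds as a conditional one. The plan names a pooled-variance test, reading Student in its usual sense, for groups whose sizes it does not control. Should size and spread both differ, the real level is not 5%, and the sign of the error is unknown beforehand. For 40 patients, normal data and an SD ratio of 1.5, the range runs from about 2% to about 11% across 3:1 splits in either direction, and the effect is small close to balance. Total size, split and SD ratio are all assumptions.

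The documents do not show that the groups will be unequal, that their spreads differ, or that any PCR result will be wrong. The case for change is that the alternative stays near 5% whichever way the cohort falls, at little cost.

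**What to change.** In the PCR paragraph, replace the Student t-test with the Welch (unequal-variance) t-test for the diabetic v non-diabetic comparison. State that it is chosen in advance, not after a preliminary variance test, and that it is applied to dCt values. Fold changes can still be reported by back-transforming the estimate and its confidence interval.

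Say whether ANOVA and Dunnett's test have any role, since the Statistical analysis section defines only two populations. If more than two groups are ever compared, use Welch's ANOVA, then Welch comparisons of each group against the control with a multiplicity adjustment. State also that this rule, and not Kruskal-Wallis, governs the PCR outcomes, so that the two sections agree.

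Cost: a few lines of wording and no new data. SPSS, the named software, prints the Welch result beside the Student result as the line for unequal variances. The downside is about 3 points of power (73% v 76%) if variances are equal at 3:1. Handling of repeated biopsies from one patient needs its own statement; this change does not supply it.

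### Progression in the graft is an aim and every graft is biopsied from the first weeks, but no change measure is defined and no named test uses the graft's own first value

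*Combined protocol and SAP*

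**What the plan says.** - **Aim (Background).** After the aim for the explanted hearts, the plan adds that "the progression of such lesions in the transplanted heart in diabetic patients will be evaluated". The official title concerns lipid accumulation in hearts from non-diabetic donors.
- **Biopsies (Endo-myocardial biopsies and Follow up).** "In all transplanted patients endo-myocardial biopsies (EMB) are collected according to normal clinical practice", and the schedule starts "weekly for the first month; every 2 weeks for the following month". Tissue left after rejection histology goes to research: "From the remaining portion of tissue 3 portions will be obtained: one portion will be incorporated into the OCT compound for immunohistochemical analysis", with the other two for PCR and ELISA.
- **Lipid measure (Immunohistochemistry).** Oil Red O "will be used for the assessment of the accumulation of intramyocytic lipids". No scale, time point or change measure is given.
- **Gene expression (PCR).** "P values will be calculated on the basis of a student t-test or one-way variance analysis (ANOVA), followed by Dunnett's post hoc test". Neither the Dunnett control nor the calibrator for the relative quantification is named.
- **Group comparisons (Statistical analysis).** Groups "will be compared using the Pearson test for categorical variables and the Kruskal-Wallis test for continuous variables". The section adds: "All tests will be conducted in 2 populations: diabetic vs non-diabetic patients after cardiac transplantation". The only covariate adjustment is in the mortality Cox model, and no biopsy value is among its listed covariates.

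**The concern.** Progression is change within a graft over time. A level measured months after transplant is the graft's starting value plus whatever has changed since. The explanted heart cannot supply that starting value, because it is the recipient's own organ and not the graft. The early biopsies can, at least approximately, and the plan already collects them.

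Comparing levels alone has two consequences. First, the result does not answer the stated question: a group difference in level is not a difference in progression, and it says nothing about change within diabetic recipients. Second, variation between grafts in their starting value stays in the error term. That matters in a single-centre transplant cohort with no stated sample size, where patients cannot readily be added.

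**Working it through.** The plan states no sample size, effect size, standard deviation (SD) or power, so there is no figure to reproduce.

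**Inputs from the documents:** an early biopsy in every graft; between-group tests without a baseline; significance level 0.05 (taken as two-sided; sidedness is not stated).

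**Assumptions, not from the documents:** correlation ρ between first and later biopsy of 0.3 to 0.7; true group effect of 0.5 or 0.8 SD; 30 patients per group for power; equal variances at the two times.

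**Step 1: variance of the group difference, relative to comparing levels (= 1).**
- Change from first biopsy: 2(1 − ρ).
- Baseline-adjusted (ANCOVA): 1 − ρ². Equivalent gain in sample size: 1/(1 − ρ²).

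**Step 2: patients per group for 80% power at 0.8 SD.** n = 2 × (1.960 + 0.842)² × factor / 0.8², rounded up. With factor 1 this is 24.5, so 25.

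**Step 3: power at 30 per group and 0.5 SD.** Φ(0.5 × √(30/2) / √factor − 1.960). With factor 1 this is Φ(1.936 − 1.960) = 49%.

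| ρ | Adjusted factor | Variance removed | Equivalent gain in patients | n per group: levels / adjusted / change | Power: levels → adjusted |
|---|---|---|---|---|---|
| 0.3 | 0.91 | 9% | 10% | 25 / 23 / 35 | 49% → 53% |
| 0.5 | 0.75 | 25% | 33% | 25 / 19 / 25 | 49% → 61% |
| 0.7 | 0.51 | 49% | 96% | 25 / 13 / 15 | 49% → 77% |

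A plain change score has a factor of 1.4 at ρ = 0.3, so it is less precise than comparing levels whenever ρ is below 0.5.

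**Step 4: simulation** (normal data, 30 per group, 3,000 runs per setting). At 0.5 SD, Kruskal-Wallis on levels had 45–47% power, and ANCOVA had 51%, 59% and 76% at ρ = 0.3, 0.5 and 0.7. A small part of that gap is the move from a rank test to a parametric one; Step 3 compares like with like.

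**Step 5: false-positive rate with no true difference in progression.** Each range covers ρ = 0.3 to 0.7.

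| Persistent group difference at implant (assumed) | Kruskal-Wallis on levels | Kruskal-Wallis on change | ANCOVA |
|---|---|---|---|
| None | 4–5% | 5% | 5% |
| 0.3 SD | 19–21% | 5% | 8–13% |
| 0.5 SD | 45–46% | 5% | 12–27% |

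ANCOVA leaves a residual bias of b(1 − ρ) when the groups differ by b at implant and the difference persists. For b = 0.3 SD this is 0.21, 0.15 and 0.09 SD at ρ = 0.3, 0.5 and 0.7. With no group difference at implant, all three methods hold the nominal 5%, and the only cost of comparing levels is precision.

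**The case against.** **The plan does not say that later levels are compared.** This is correct. The Statistical analysis section names no tissue measure, biopsy or time point. Its next sentence selects candidates for the multivariate model, so the tests may mainly concern patient characteristics. Kruskal-Wallis could also be run on change values. A reader might infer a stated rule to ignore the first biopsy; there is none. What stands is that no change measure is defined and no other test is offered, so levels is the plain reading.

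**Gene expression has its own tests.** Dunnett's control group or the calibrator could in principle be the first biopsy. The PCR section does not say so, Oil Red O would not be covered, and one-way ANOVA would ignore the pairing within a graft.

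**Implant lipid may not bias anything.** A reader might infer that any chance imbalance at implant would be passed off as a diabetes effect. It can shift a single study's estimate, but the test's 5% error rate already allows for it, as the first row of Step 5 shows. Inflation needs a systematic group difference at implant. The documents show none, and the title's non-diabetic donors make a large one less likely. Recipients are not randomised to donors, so it cannot be excluded either.

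**The first biopsy is an imperfect baseline.** It is not taken at implant, and nothing in the documents shows that recipient diabetes has had no effect by then. Research tissue is what remains of 1–3 mm³ fragments, split three ways, so values may be noisy or missing. Both points stand. Noise lowers ρ, and at ρ = 0.3 the gain is small.

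**Conclusion.** The concern holds as a mismatch between aim and analysis. The plan asks about progression, schedules the biopsies needed to measure it, and names only tests that, as described, use no baseline. The harm that can be asserted is that progression goes unmeasured and precision is lost. The loss depends entirely on the assumed correlation: 9% of variance at 0.3, 25% at 0.5 and 49% at 0.7, equivalent to 10%, 33% and 96% more patients.

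The documents do not support a claim that the planned comparison is biased. The false-positive rates of 19–21% and 45–46% in Step 5 apply only under an assumed persistent implant difference of 0.3 or 0.5 SD. They are a reason to include a change-score sensitivity analysis, not evidence of bias in this study.

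**What to change.** Add to the Statistical analysis section, for each continuous graft-tissue measure including gene expression, and replacing the PCR section's tests for graft biopsies:

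> The earliest evaluable biopsy in the first month is the graft baseline. Log-scale values from later biopsies are analysed in a mixed model with a patient-level random effect, baseline as covariate, and group, time and group-by-time terms. The primary time point is the biopsy nearest 12 months, within a stated window. We report the baseline-adjusted ratio of diabetic to non-diabetic recipients with 95% CI, and the within-group change in diabetic recipients with 95% CI. Change from first biopsy is a sensitivity analysis, because groups are not randomised.

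The window is needed because the eight scheduled biopsies run to about week 18 (4 + 4 + 4 + 6 weeks). Three-monthly biopsies then fall near weeks 31, 44 and 57, so none is at week 52. The SAP should also state the Oil Red O scale and how zero values are handled on the log scale. A graded score would need an ordinal model instead.

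The cost is analysis wording only, with no added biopsy or visit. Downsides to state in the SAP: any diabetes effect already present at the first biopsy is adjusted away; a small leftover sample may make the baseline noisy or missing, which lowers the gain; and adjustment reduces but does not remove bias from a true implant difference. The number of recipients without an evaluable first-month biopsy should be reported by group.
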